14.2.4 Safety Analysis

Extent of Exposure – Duration (number of cycles/infusions) of decitabine doses (cumulative and intensity) will be summarized.

Adverse Events - All adverse events will be coded using NCI CTCAE v. 4.0. The incidence of treatment-emergent adverse events (number and percent of patients reporting the adverse event at least once during the study) will be summarized. In addition, adverse events will be summarized by investigator attribution of relationship to study medication and by grade. Similar summaries will be provided by treatment cycle.

Clinical Laboratory Evaluation – Applicable laboratory parameters will be graded according to NCI CTCAE version 4.0. The incidence of maximum grade (number and percent of patients experiencing the maximum grade during the study) will be summarized for each laboratory parameter. Similar summaries will be provided by treatment cycle. Graphical displays of select hematological parameters will also be provided.

Vital Signs, Physical Findings, and Other Safety Observations – Vital signs, findings from physical examinations, ECOG scores and weights will be presented in listing format.

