3.0 PATIENT SELECTION

3.1 Inclusion Criteria

All of the following:

- Patient must have non-M3 AML or MDS
- An adverse risk karyotype defined by:
 - Complex karyotype by cytogenetics, or
 - Deletion of all or part of chromosome 5, 7, 12, or 17 defined by FISH or cytogenetics, or
 - Somatic TP53 mutation

All of the following:

1. Patient must have an ECOG performance status ≤ 2 .
2. Patient must have $>10\%$ disease burden measured by cytomorphology, flow cytometry, or cytogenetics.
3. Patient must have peripheral white blood cell count $\leq 50,000/\text{mcl}$.
4. Patient must have adequate organ function, defined as:
 - a. Total bilirubin $\leq 1.5 \times \text{ULN}$
 - b. AST/ALT $\leq 2.5 \times \text{ULN}$
 - c. Serum creatinine $\leq 2.0 \times \text{ULN}$
5. Patient must have undergone ≤ 2 cycles of prior hypomethylating agent (decitabine or azacitidine).
6. Patient must be enrolled in HRPO# 201011766 (“Tissue Acquisition for Analysis of Genetic Progression Factors in Hematologic Diseases”).
7. Patient must be ≥ 18 years of age.
8. Patient must be able to understand and willing to sign an IRB-approved written informed consent document.

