5.0 INVESTIGATIONAL PLAN

5.1 Summary of Study Design

This is an open-label, single-arm, Phase II, biomarker study of patients with AML or MDS who are treated with 10 consecutive days of decitabine. FAB-M3 AML is excluded from this trial, because other well-tolerated options exist for the treatment of FAB-M3 acute promyelocytic leukemia. AML patients who are < 60 years old and have not received cytotoxic induction chemotherapy are also excluded, because cytotoxic therapy offers a curative possibility for these patients. MDS patients without cytopenias are also excluded because these patients can be followed with watchful-waiting.

All patients will undergo bone marrow biopsies pre-study, on Cycle 1 Day 10 \pm 1, and on Day 28 \pm 4 of Cycles 1, 2, 4, and 6. Following Cycle 6, bone marrow biopsies should be performed at the discretion of the treating physician to assess for relapse or progression. Patients will provide a skin biopsy sample pre-study. See Section 8.0 for details on correlative studies.

Patients will receive decitabine 20 mg/m²/day as a 1-hour infusion on consecutive Days 1-10 in 28-day cycles. The dose will be calculated based on actual patient weight at the beginning of each cycle.

Once AML patients achieve morphologic complete remission with incomplete blood count recovery (CRi) or MDS patients achieve a marrow complete response (Marrow CR) as defined in Section 9.0, decitabine administration may be decreased to 20 mg/m²/day for ten consecutive days every 6 weeks, to limit myelosuppressive toxicity and improve count recovery. After 2 cycles at 6 week intervals, the dose may be reduce to 20 mg/m²/day for five consecutive days in 6 week cycles, at the discretion of the treating physician. After two cycles of five consecutive days of treatment, if the patient meets the definition of CR with complete cytogenetic response as defined in Section 9.0, administration may further be decreased to three consecutive days per cycle at the discretion of the treating physician.

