5.2.2 Baseline Evaluation

Baseline evaluations must take place no more than 7 days prior to the first dose of decitabine.

1. Medical history
2. Physical exam including height, weight, and ECOG performance score.
3. Record transfusion requirements for 8 weeks before first dose of study drug
4. CBC with differential and platelets
5. Serum chemistries, including bicarbonate, calcium, glucose, total protein, albumin, BUN, potassium, chloride, sodium, creatinine, total bilirubin, AST, ALT, alkaline phosphatase, LDH
6. Urine β HCG pregnancy test if appropriate
7. Clinical pathology should be carefully reviewed to rule-out acute promyelocytic leukemia (M3-AML), and discussion between the pathologist and treating physician should take place if warranted by morphology or immunophenotype.

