6.1 Delay for Cytopenia or Infection

As cytopenias are a defining feature of AML and MDS, their presence alone does not generally warrant dose modifications or delays. Patients will receive four cycles of therapy without adjustment for any cytopenia. Following Cycle 4, dose modifications or delays for cytopenias will be made at the discretion of the investigator.

Patients with febrile neutropenia (temperature $\geq 38.5^\circ$ with ANC $< 1,000/\mu\text{l}$) or systemic infections should have treatment held until clinical resolution of the infection.

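### The laboratory safety table reports maximum on-study grade with no baseline reference, so its blood-count rows cannot separate new or worsened cytopenia from cytopenia present at entry

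*Combined protocol and SAP*

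**What the plan says.** Section 14.2.4 grades laboratory values by CTCAE version 4.0 and then states: "The incidence of maximum grade (number and percent of patients experiencing the maximum grade during the study) will be summarized for each laboratory parameter". The same is repeated by cycle, and "Graphical displays of select hematological parameters will also be provided". The safety population in 14.1 is every patient who received a dose, with no restriction on baseline grade. The laboratory paragraph makes the same provision in all five protocol versions in the file. None names a shift table, a change from baseline or a rule for worsening.

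The protocol expects low counts at entry. Section 6.1 says: "As cytopenias are a defining feature of AML and MDS, their presence alone does not generally warrant dose modifications or delays". In 3.1 the entry limits under "Patient must have adequate organ function, defined as" cover bilirubin, AST/ALT and creatinine. There is also a ceiling on the white-cell count, but no floor for ANC, platelets or haemoglobin. Section 9.2.1 has haematologic-improvement rules for pretreatment haemoglobin below 11 g/dL, ANC below 1.0 and platelets below 100 x 10^9/L, with a separate platelet rule for patients starting below 20.

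A baseline reference is available. The 5.2.2 evaluation includes a CBC, and "Baseline evaluations must take place no more than 7 days prior to the first dose of decitabine". It also records transfusions over the preceding 8 weeks.

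**The concern.** A maximum-grade table can be read as drug toxicity when patients start with normal values. Here many may not. A patient who enters at grade 3 and stays there is counted in the same row as one who falls from grade 0 to grade 3.

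The blood-count rows are the ones a reader will look to. The regimen is 10 days of decitabine per cycle, and 6.1 says: "Patients will receive four cycles of therapy without adjustment for any cytopenia". The 6-week interval is offered after response in order to limit myelosuppression. A reader judging the marrow toxicity of this schedule would go to this table, and part of what it shows may pre-date the first dose. With no control arm, each patient's own baseline is the only internal reference. Section 9.2.1 already uses pretreatment values to judge benefit in these three lineages, but 14.2.4 does not use them to describe harm.

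**Working it through.** The plan states no figure for this summary, so there is nothing to reproduce. The check is algebra with assumed inputs.

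**Inputs**
- N = 25 + 100 = 125, the planned enrolment in 14.3, taken here as the safety population.
- q: share of patients at grade 3-4 at baseline for a given parameter. Not in the documents; assumed 10%, 30% and 50%.
- r: share of those patients with at least one on-study value at grade 3-4. Not in the documents; assumed 1 and 0.5. CBCs fall on Day 1 of each cycle (5.2.3) and weekly in cycle 1 (5.2.6), so recurrence is plausible. The plan does not say whether a pre-dose Cycle 1 Day 1 count is on study.
- t: rate of new grade 3-4 among patients at grade 0-2 at baseline. Not in the documents.

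**Formulae**
- Reported in the planned row: R = r·q + (1 − q)·t
- Newly grade 3-4, on the same all-treated denominator: (1 − q)·t
- Excess: R − (1 − q)·t = r·q. This does not depend on t and is at most q.

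**Results**

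| q | Excess, r = 1 | Excess, r = 0.5 | New grade 3-4 if R = 70%, r = 1 | New grade 3-4 if R = 70%, r = 0.5 |
|---|---|---|---|---|
| 10% | 10 points (12.5 of 125) | 5 points | 60% | 65% |
| 30% | 30 points (37.5 of 125) | 15 points | 40% | 55% |
| 50% | 50 points (62.5 of 125) | 25 points | 20% | 45% |

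The last two columns are 70% − r·q. A higher-q example with t = 25% is q = 60%. The row reads 0.60 + 0.40 × 0.25 = 70% if all recur and 0.30 + 0.10 = 40% if half do. Newly grade 3-4 patients are 10% in both cases.

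**What the excess measures.** It counts patients in the row who are not newly grade 3-4. It does not count patients who failed to worsen. If a share w of the baseline grade 3-4 group moves from grade 3 to grade 4, then w·q of all patients have worsened, and the planned table shows them at grade 4. At assumed q = 30%, r = 1 and w = 20%, that is 6 points. The share counted without worsening is then 30 − 6 = 24 points.

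**The case against.** The strongest reply is that the size is wholly assumed. The documents give neither q nor the CTCAE cut-offs. Expecting cytopenia is not the same as entering at grade 3-4. That stands: if q is near zero, the point disappears.

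A reader might also infer that entry cytopenia is a requirement for MDS patients, because 5.1 says: "MDS patients without cytopenias are also excluded because these patients can be followed with watchful-waiting". The version printed first in the file, taken here as current, does not carry that exclusion into 3.1 or 3.2. Its 3.1 asks for AML or MDS with adverse-risk cytogenetics or a TP53 mutation. MDS count thresholds appear in 3.1 only in other versions. The premise therefore rests on 6.1, on the absence of count minima in 3.1, and on 9.2.1.

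Other outputs help in part. The adverse event paragraph says: "The incidence of treatment-emergent adverse events (number and percent of patients reporting the adverse event at least once during the study) will be summarized". Attribution and grade are reported too, but no baseline comparison is stated. The content of the graphs is left open. Baseline laboratory values are part of the safety evaluation (9.4.3), and 14.2.1 summarises baseline characteristics. That could show entry counts for the group, but not which patients worsened.

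Finally, the table is labelled as maximum grade and does not claim to count new toxicity. No stated decision uses it: safety is not a listed objective in 2.1 or 2.2, and the dosing rules are already fixed. This limits the weight of the point. It does not make the table able to answer the question a reader will bring to it.

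**Conclusion.** The point holds as a minor, inexpensive improvement. As planned, the ANC, platelet and haemoglobin rows can mix entry cytopenia with on-study cytopenia, and no other planned output is specified in a way that separates them.

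The excess over newly grade 3-4 patients is r·q. It is at most q, equals q only if every patient at grade 3-4 at baseline shows that grade again on study, and is q/2 if half do. Every percentage above is illustrative.

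Three stronger readings are not supported:
- That a known or large share of patients enters at grade 3-4. No document gives that share.
- That the excess is always the whole of q, or that all of q are patients who did not worsen. The first needs full recurrence on study; the second ignores moves from grade 3 to grade 4.
- That the trial's conclusions are at risk. The effect is confined to descriptive safety reporting; the primary objective and sample size are untouched.

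**What to change.** Keep the maximum-grade table. For ANC, platelets and haemoglobin, add a shift table of baseline grade by worst post-dose grade. Baseline is the last value before the first dose, from the 5.2.2 CBC; this also settles how a pre-dose Day 1 count is handled. From it report:
- (a) patients whose grade worsened from baseline, including grade 3 to grade 4;
- (b) new grade 3-4 among patients at grade 0-2 at baseline, with that denominator shown.

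Footnote that transfusion, hydrea, growth factors and disease progression all affect the grades, so worsening is not a pure drug effect.

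The cost is analysis-plan wording and table shells; no new data are needed. There are two downsides.

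First, the denominator for (b) shrinks to (1 − q) × 125 = 112.5, 87.5 or 62.5 at q = 10%, 30% or 50%. The 95% half-width at a 50% rate, 1.96 × √(0.25/n), is then 9.2, 10.5 or 12.4 points, against 8.8 at 125.

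Second, some misclassification remains. Suppose a share m of patients truly at grade 3-4 read as grade 0-2 at baseline after transfusion and later show grade 3-4. Then m·q of all patients are wrongly called new. At assumed q = 30% and m = 10%, 20% or 30%, that is 3, 6 or 9 points, against up to 30 in the planned row. On the at-risk denominator, with m = 20% and t = 40%, the estimate is (0.70 × 0.40 + 0.06) / (0.70 + 0.06) = 44.7% instead of 40%.

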14.2.5 Description of Planned Subgroup Analyses

The following subgroups (if sufficient numbers of patients) will be explored with respect to the primary and overall survival endpoints.

- Age (60-69 years old vs ≥ 70 years old)
- Cytogenetics
- Patients with AML-associated mutations in *DNMT3A*, *TET2*, *IDH1*, or *IDH2* vs those who do not have somatic variants in these genes.

14.3 Sample Size

We anticipate initially enrolling 25 patients at Washington University. Once we establish a routine exome analysis with validation and calculation of the rate of patient-specific mutation clearance, we will enroll an additional 100 patients from at least 2 additional centers.

15.0 DATA SUBMISSION SCHEDULE

Case Report Form	Submission Schedule
Original Consent Form	Prior to registration
Patient Registration Form Disease Diagnosis Form Inclusion Criteria Worksheet Exclusion Criteria Worksheet	Prior to starting treatment
Treatment Record Form	To be maintained throughout a patient's treatment cycle. The complete record is due at completion of treatment.
Bone Marrow Sample Collection Form	To be maintained throughout the course of the study at designated bone marrow sample collections time points (See Appendix 2).
Pathology: Bone Marrow Biopsy	To be completed upon the return of pathology report for each bone marrow biopsy.
Study Calendar Form	To be completed with the date of each time point upon occurrence.
Labs Form	To be completed upon the return of laboratory reports for each study time point (See Appendix 2)
Dose Modifications	To be maintained throughout the course of the study if dose modifications are performed.
Therapy Response Form	To be filled out upon remission (prior to, and/or on therapy)
End of Study Form	Due at the completion of the EOS visit, at the time of death, and/or at the time that the patient is lost to follow-up
Follow Up Form	
 • 30 days post date of last decitabine dose. • Every 6 months for 2 years after the last dose of study drug.
Record of Adverse Events	At the time of any AE

Any queries generated by Washington University must be responded to within 28 days of receipt by the participating site. The Washington University research team will conduct a regular review of data status at all secondary sites, with appropriate corrective action to be requested as needed.

Appendix 1 ECOG Performance Scale

Activity Status	Description
0	Asymptomatic, fully active, and able to carry on all predisease performance without restrictions.
1	Symptomatic, fully ambulatory but restricted in physically strenuous activity and able to carry out performance of a light or sedentary nature, eg, light housework, office work.
2	Symptomatic, ambulatory and capable of all self-care but unable to carry out any work activities. Up and about more than 50% of waking hours: in bed less than 50% of day.
3	Symptomatic, capable of only limited self-care, confined to bed or chair more than 50% of waking hours, but not bedridden.
4	Completely disabled. Cannot carry on any self-care. Totally bedridden.
5	Dead

Appendix 2 Study Flow Chart

Study Flow Chart

Test	Pre-study ¹	Base-line ²	All Cycles Day 1	All Cycles Days 1-10 ³	Cycle 1 Day 4 ± 1	Cycle 1 Day 10 ± 1 and 28 ± 4	Every week	Every 2 weeks	Even cycles Day 28±4	End of Study
Informed Consent	X									
Medical History		X								
Physical Exam		X ^a	X ^b							X
Transfusion Requirements ^c		X ^c	Ongoing							
Bone Marrow Aspirate and Biopsy	X ^d					X ^d			X ^d	X ^d
Flow Cytometry ^c	X									
Pregnancy test		X								
CBC with differential and platelets		X	X				X ^f			X
Serum Chemistries ^g		X	X					X ^f		X
Decitabine administration ^h				X						
Adverse Events			Ongoing							
Post-study follow-up										X ⁱ

¹ To be performed within 28 days of the first dose of decitabine.

² To be performed within 7 days of the first dose of decitabine.

³ Decitabine may be reduced to Days 1-5 or Days 1-3. See Section 6.3 for details.

^a To include height, weight, and ECOG.

^b To include weight.

^c Care should be given to record the frequency of transfusions from 8 weeks prior to first dose of study drug through the duration of the study.

^d Bone marrow biopsy and aspirate should be performed at baseline, at Cycle 1 Day 10 ± 1, and at Day 28 ± 4 of Cycles 1, 2, 4 and 6 for clinical disease assessment. Patients who achieve with clinical response (CRi or better) and are receiving cycles every 6 weeks, will undergo bone marrow biopsies on day 42 ± 4. Following Cycle 6, bone marrow biopsies should be performed at the discretion of the treating physician to assess for relapse or progression. Standard bone marrow procurement procedures will be followed for collection of the tissue. To include: correlative studies (collected under HRPO# 201011766), morphologic assessment, cytogenetics and FISH at all time points. A skin biopsy sample (collected under HRPO# 201011766) is required at pre-study, but may have been collected months or even years prior to first dose of decitabine.

^e On bone marrow or peripheral blood.

^f After Cycle 1, these labs may be obtained every other week (CBC) or once a month (Chemistries) at the discretion of the treating physician.

^g Serum chemistries include bicarbonate, calcium, glucose, total protein, albumin, BUN, potassium, chloride, sodium, creatinine, total bilirubin, AST, ALT, alkaline phosphatase, and LDH.

^h Decitabine treatment will be 20 mg/m² over a 1-hour IV infusion on consecutive Days 1-10 every 28-day cycle. The dose will be calculated based on actual patient weight at the beginning of each cycle. Patients may be premedicated with lorazepam, prochlorperazine, palonosetron, or ondansetron at the treating physician's discretion.

ⁱ Patients will be followed for 30 days following the date of the last decitabine dose to monitor for toxicity, survival and response. Thereafter, the investigator or designee will record information on subsequent therapy, disease progression, and death, every 6 months for 2 years after first dose of study drug or until the patient is lost to follow-up.

The information contained in this document is regarded as confidential and, except to the extent necessary to obtain informed consent, may not be disclosed to another party unless law or regulations require such disclosure. Persons to whom the information is disclosed must be informed that the information is confidential and may not be further disclosed by them.

Study Schema:

Patients with progressive disease after two cycles (defined as a clear increase in bone marrow blast count, typically a > 50% increase in bone marrow blasts over baseline) should be removed from study.

Patients with stable disease may continue on study and should undergo a diagnostic bone marrow biopsy at the end of even numbered cycles.

Once AML patients achieve morphologic complete remission with incomplete blood count recovery (CRi) or MDS patients achieve a marrow complete response (Marrow CR) as defined in Section 9.0, decitabine administration may be decreased to 20 mg/m²/day for ten consecutive days every 6 weeks, to limit myelosuppressive toxicity and improve count recovery. After 2 cycles at 6 week intervals, the dose may be reduce to 20 mg/m²/day for five consecutive days in 6 week cycles, at the discretion of the treating physician. After two cycles of five consecutive days of treatment, if the patient meets the definition of CR with complete cytogenetic response as defined in Section 9.0, administration may further be decreased to three consecutive days per cycle at the discretion of the treating physician.

Sample collection for correlative studies:

Bone marrow biopsies should be performed at baseline, at Cycle 1 Day 10 ± 1, and at Day 28 ± 4 of Cycles 1, 2, 4, and 6. Following Cycle 6, bone marrow biopsies should be performed at the discretion of the treating physician to assess for relapse or progression.

Genomic Predictors of Decitabine Response in AML/MDS

Table of Contents

Section	Page
1.0 INTRODUCTION.....	7
1.1 Rationale.....	7
1.2 Decitabine and Hypomethylating agents in AML/MDS.....	9
1.2.1 Pharmacokinetics and Metabolism of Decitabine.....	11
1.2.2 Experience with extended dosing schedules.....	12
1.3 Correlative Studies.....	13
2.0 OBJECTIVES.....	15
2.1 Primary Objective.....	15
2.2 Secondary Objectives.....	15
3.0 PATIENT SELECTION.....	16
3.1 Inclusion Criteria.....	16
3.2 Exclusion Criteria.....	16
3.3 Inclusion of Women and Minorities.....	17
4.0 REGISTRATION PROCEDURES.....	18
4.1 Confirmation of Patient Eligibility.....	18

1.0 INTRODUCTION

[figure not shown]
1.1 Rationale

[figure not shown]
Personalized therapy for cancer requires that 1) patient-specific factors (e.g. patient-specific mutations, expression profiles, or pharmacogenomics) influence treatment algorithms, and 2) once therapy is initiated, *in vivo* responsiveness is used to guide further therapy. The modern era of genomics has provided significant insights into cancer pathogenesis by describing patterns of germline and somatic variants, as well as defining disease-specific patterns of gene expression. However, the application and integration of this data with therapeutics remains a difficult task.

AML and MDS are two closely related hematological disorders characterized by ineffective hematopoiesis and malignant expansion of clonal myeloid cells. Both AML and MDS frequently occur in elderly patients and some cases are secondary and/or related to long-term bone marrow damage after radiation or chemotherapy. Current therapy for AML consists of cytotoxic chemotherapy followed by consolidation chemotherapy or stem cell transplantation. Using these approaches, current cure rates may be as high as 60% for patients younger than 60 with good risk cytogenetics (e.g. t(15;17), t(8;21), inv(16)).[4] Outcomes in patients ≥ 60 years old and with relapsed disease remain poor with 2 year survival of only ~25%.[5] Historically, the available treatment for MDS has been symptomatic and has not been shown to be effective in producing sustained improvement in hematopoiesis or in delaying leukemic evolution[6, 7].

Current AML therapy is poorly tolerated in elderly and pre-treated patients due to hematologic and non-hematologic toxicities; following such therapy, patients typically require 3-4 weeks of hospitalization for treatment of neutropenic fevers and for regular transfusions. Even among the relatively healthy patients enrolled in clinical trials, induction mortality in the elderly can be as high as 20-40% following standard induction therapy,[8-11] and moderate to severe non-hematologic toxicity occurs in at least an additional 30% of patients.[9, 12-14] Consequently, many older AML patients are not offered traditional intensive chemotherapy, but receive supportive care alone.[15] More effective and less toxic therapies are needed to provide durable remissions in a significant proportion of elderly AML in populations.

We and others have recently used whole genome sequencing to identify recurrent, somatic mutations in AML and MDS patients in four genes that are involved in methylcytosine regulation: *DNMT3A*, *IDH1*, *IDH2*, and *TET2*. [29-37] Collectively, nearly half of all AML/MDS patients have a mutation in one of these four genes. *DNMT3A* mutations are associated with an adverse outcome in AML patients treated with cytotoxic chemotherapy. [35, 38] However, it is not yet clear whether the presence of mutations in one or more of these genes is associated with response or resistance to decitabine.

In this study, we will treat patients with the current state-of-the-art decitabine schedule. [3] We will perform exome sequencing on all patients and correlate response with mutation status, rate of mutation clearance, expression profile, plasma decitabine levels, and DNA

methylcytosine content reduction. This approach will comprehensively assess genomic and pharmacologic parameters that could clinically predict patient response to decitabine.

In this study, we will combine analysis of patients with AML and MDS. Recent genomic analysis has shown that AML and MDS have shared mutations in many of the same genes, shared patterns of mutation acquisition, and shared patterns of mutation evolution.[39, 40] Furthermore, MDS, like AML, presents with clonal hematopoiesis, even when the morphologic blast count is zero.[36] Because this study will identify and track the rate of clearance of patient specific mutations, and because decitabine has been shown to have efficacy in both AML and MDS patients, [2, 3, 16-19, 41-45] combining analysis of AML and MDS patients is reasonable. Asymptomatic MDS patients are excluded because these patients are typically followed with watchful-waiting rather than with chemotherapy.

